## **9.10 Handling and Disposal**

Investigational product reconciliation must be performed at the site by the unblinded pharmacist(s) or appropriately qualified individual(s) using treatment log forms or within the IRT system. After reconciliation authorization by the Sponsor, all used, partially used, and unused vials and all original packaging will be disposed of by the Sponsor or per the site's standard practice. This process will be provided to the site by the Sponsor's designee.

## **9.11 Permitted and Prohibited Therapies**

All non-study therapies including but not limited to over the counter and non-pharmacological treatments from the time of Screening (Visit 1) and through the end of study must be recorded on the appropriate eCRF page. Record of ICS and LABA use should be captured for the three months immediately prior to Screening.

### **9.11.1 Prior Therapies**

Prior therapies include all therapies received from the Screening Visit (Visit 1) to just prior to 1st dose of study drug, with the exception of ICS and LABA which should also be recorded for the 3 months immediately prior to Screening (Visit 1). Prior therapy information must be recorded on the appropriate eCRF page.

### **9.11.2 Concomitant Therapies**

Concomitant therapies refer to all therapies taken on or after the first dose of study drug through

the last visit. Concomitant therapy information must be recorded on the appropriate eCRF page.

### **9.11.3 Permitted Therapies**

Medications considered necessary for the subject's welfare, may be administered at the discretion of the investigator. The medical monitor should be contacted in the event the site is in a situation where further clarity is needed.

Acceptable methods of birth control considered to be highly effective (e.g., results in a low failure rate [i.e., <1% per year]) when used consistently and correctly, include oral/injectable/inserted/implanted/ transdermal contraceptives, condom with diaphragm, condom with spermicide, diaphragm with spermicide, intrauterinehormone-releasing system or IUD, or sexual abstinence.

### **9.11.4 Prohibited Therapies**

During the study, new initiation of investigational compounds or concomitant treatment with other asthma therapy is not permitted. The use of systemic corticosteroids, biologics, immunosuppressants and inhaled anticholinergics is not permitted. Subjects who require systemic corticosteroids or another non-study asthma medication to treat an asthma exacerbation should be withdrawn from the study. If a subject receives a systemic corticosteroid for another reason (e.g., bee sting), the Medical Monitor should be consulted regarding the subject's continuation in the study.

Leukotriene inhibitors are not allowed to be added to a subject's treatment regimen after they are screened for the study. Subjects who are on leukotriene inhibitors as part of their prior therapy at Screening (Visit 1) may continue on leukotriene inhibitors during the course of study participation.

## **9.12 Treatment after End of Study**

Subjects will be treated per standard clinical practice following completion of participation in the study.

## **10 STUDY PROCEDURES**

Subjects will provide written informed consent before any study-related procedures are initiated.

For the timing of assessments and procedures throughout the study, refer to the schedule of assessments ([Table 1](#)). Throughout the study, every reasonable effort should be made by study personnel to follow the timing of assessments and procedures in the schedule of events for each subject. Visits performed after Visit 2 should be scheduled relative to Visit 2. If a subject misses a study visit for any reason, the visit should be rescheduled as soon as possible. Permitted visit windows are noted in the schedule of assessments ([Table 1](#)).

In the event a subject cannot be in-clinic for a study visit after randomization due to pandemic, natural disaster, or other kinds of unforeseeable situations, sites should attempt to complete as many visit procedures as possible that can be done remotely, by phone or telehealth/video, on time and per protocol windows. This includes completion of study-required questionnaires which should be provided to the subject or reviewed via phone prior to the visit, if possible, so that the subject can be prepared with appropriate responses.

The medical monitor should be consulted for decisions regarding dosing, laboratory testing, and other protocol procedures which are unable to be done remotely.

If a visit is done remotely, it should be documented as such in subject source records.

## 10.1 Study Duration

AVTX-002 and placebo treatment will be administered at Visit 2 (Day 0), Visit 5 (Day 28), and Visit 7 (Day 56). **A subject may not be dosed after Day 56.** The duration of the treatment period is considered 84 days, with each dose of study drug considered to be 28 days of treatment. The overall study period is approximately 135 days, including Screening and the 30-day, stabledose, run-in period.

## 10.2 Assessments

### 10.2.1 Medical History

A medical and surgical history will be taken at Screening. All significant medical history findings that have been present or active within the 5 years prior to screening will be entered into the eCRF. Medical history findings that have not been present within the 5 years prior to screening will be recorded if deemed clinically relevant by the investigator to the conduct of the study.

Additionally, the subject's overall NEA history will be captured at Screening. This includes but is not limited to the approximate date of diagnosis and prior treatment including approximate start and stop dates.

### 10.2.2 Efficacy

Efficacy response will be assessed by the procedures listed below at the time points mentioned in the schedule of assessments ([Table 1](#)).

#### 10.2.2.1 Asthma Related Events

The proportion of patients who experience any of the following asthma related events and time to the asthma related event will be determined:

- $\geq 6$  additional reliever puffs of SABA (compared to baseline) in a 24-hour period on 2 consecutive days or,
  - Baseline SABA use (defined as the number of individual puffs or inhalations taken by the subject) will be determined by the average use in the 7 days preceding Visit 2,
- increase in ICS dose  $\geq 4$  times than the dose at baseline or,
  - Baseline ICS dose is defined as the dosage the subject received during the 30-day run-in period,
- a decrease in peak flow of 30% or more (compared to baseline) on 2 consecutive days of treatment or,
  - Baseline peak flow will be determined by the average of measurements in the 7 days preceding Visit 2.
- an asthma exacerbation requiring the use of systemic corticosteroids (tablets, suspension, or injection) for at least 3 days or
- a hospitalization or emergency room visit because of an asthma exacerbation.

Time to event will be measured in days using the first day of the event above to denote the day of the overall asthma related event occurrence.

Subjects meeting any of the above criteria for an asthma related event will be permitted to restart background (pre-study) therapy, or alternate asthma therapy. If background/alternate therapy is reinitiated/started, the patient must be withdrawn from the study.

#### **10.2.2.2 Forced Expiratory Volume in 1 Second (FEV1)**

The FEV1 is the volume of air that can be forcibly exhaled from the lungs in the first second, measured in liters by a spirometer and reported as a percent of expected volume.

#### **10.2.2.3 Fractional Exhaled Nitric Oxide (FeNO)**

A FeNO test measures the levels of nitric oxide during exhalation. A FeNO test will be done by breathing into a tube attached to a hand-held monitor.

#### **10.2.2.4 Peak Flow Meter**

A peak flow meter measures how well lungs are able to expel air. Subjects will measure peak flow daily on a device provided by the Sponsor and record the results in their diary. The site will monitor the diary entries closely to assess subject compliance. Subjects who are not compliant with the diary will be counseled by the site and will be considered protocol deviations if an overall compliance rate of less than 80% is reached.

#### **10.2.2.5 Asthma Control Questionnaire (ACQ)**

This is a simple questionnaire to measure the adequacy of asthma control and change in asthma control. ACQ has a multidimensional construct assessing symptoms (5 items, self-administered), rescue bronchodilator use (1 item, self-administered), and FEV1 (1 item, completed by study staff). Scores range between 0 (totally controlled) and 6 (severely uncontrolled) (Juniper et al, 2005).

#### **10.2.2.6 Standardized Asthma Quality of Life Questionnaire for 12 years and older (AQLQ(S)+12)**

The AQLQ(S)+12 is a modified version of the standardized AQLQ, which was developed to measure functional impairments experienced by adults aged  $\geq 17$  years. The AQLQ(S)+12 is valid for patients aged 12 to 70 years and includes 32 questions in 4 domains (symptoms, activity limitation, emotional function, and environmental stimuli) (Juniper et al, 1992; Wyrwich et al, 2011).

Subjects will be asked to recall their experiences during the previous 2 weeks and score each of the questions on a 7-point scale, where 7=not at all limited and 1=totally limited. The overall score of the AQLQ +12 will be derived as the average of the 32 questions; thus, the total score ranges from 1 (indicates "total impairment") to 7 (indicates "no impairment").

#### **10.2.2.7 Asthma Symptom Diary**

The Asthma Symptom Diary is a 6-item daily measure of asthma symptom severity that assesses three core categories of asthma symptoms: breathing symptoms (difficulty breathing; wheezing; shortness of breath), chest symptoms (chest tightness; chest pain), and cough. The Asthma Symptom Diary is intended for twice daily completion and comprises a morning diary (for completion upon waking and referring to asthma symptoms during the nighttime) and an evening diary (for completion before going to bed and referring to asthma symptoms during the day). Subjects are required to rate the 6 symptoms at their worst during the respective timeframes using an 11-point numeric rating scale ranging from 0 ('None') to 10 ('As bad as you can imagine') (FDA, n.d.). The site will monitor the diary entries closely to assess subject compliance. Subjects who are not compliant with the diary will be counseled by the site and will be considered protocol deviations if an overall compliance rate of less than 80% is reached.

#### **10.2.2.8 European Quality of Life – 5 Dimension 5 level Questionnaire (EQ-5D-5L)**

The EQ-5D-5L consists of the EQ-5D descriptive system and the EQ visual analogue scale (EQ

VAS). The descriptive system comprises five dimensions: mobility, self-care, usual activities, pain/discomfort, and anxiety/depression. Each dimension has 5 levels: no problems, slight problems, moderate problems, severe problems, and extreme problems. The EQ VAS records the subject's self-rated health on a vertical VAS, where the endpoints are labelled 'The best health you can imagine' and 'The worst health you can imagine' ([EuroQol, 2017](#)).

#### **10.2.2.9 Patient Global Impression of Change/Severity**

The Patient Global Impression of Change or Severity (PGI-C, PGI-S) scale is a global index that can be used to rate the severity of a specific condition (a single-state scale) from the patient's perspective. The PGI-C is a single question scale asking the patient to rate the overall status of their specific condition on a 7-point scale. The PGI-S is a single questionscale asking the patient to rate current state of their specific condition on a 7-point scale.

#### **10.2.2.10 Clinician Global Impression of Improvement/Severity**

The Clinician Global Impression of Improvement or Severity (CGI-I, CGI-S) is a global index that can be used to rate the severity of a specific condition (a single-state scale) from the clinician's perspective. The CGI-I is a single question scale asking clinician to rate the overall status of the patient's specific condition on a 7-point scale since the beginning of the research study. The CGI-S is a single question scale asking the clinician to rate current state of the patient's specific condition on a 7-point scale.

#### **10.2.2.11 Short-Acting Beta Agonist Use**

The number of times a short-acting beta agonist (number of inhalations/puffs) is used will be assessed by reviewing the diary maintained by the subject. The site will monitor the diary entries closely to assess subject compliance. Subjects who are not compliant with the diary will be counseled by the site and will be considered protocol deviations if an overall compliance rate of less than 80% is reached.

### **10.2.3 Safety**

Safety and tolerability assessments will include the frequency and severity of AEs as well as the evaluation of changes in clinical laboratory values, vital signs, and physical examination findings.

#### 10.2.3.1.2 Sampled Blood Volume

The sampled blood volume for this study is shown in [Table 2](#).

**Table 2: Sampled Blood Volume per Subject**

Assessment	Sample Volume (mL)	Number of samples	Total Volume (mL)
Chemistry	3.5	8	28.0
Hematology	2.0	8	16.0
ADA	4.5	7	31.5
Serum LIGHT	3.5	7	24.5
Inflammatory proteins	3.5	5	17.5
Immunophenotyping of circulating immune cells	10.0	3	30.0
Plasma AVTX-002	4.5	7	31.5
Total (approximate)	31.5	45	179

ADA=anti-drug antibody; LIGHT=Lymphotoxin-like, exhibits Inducible expression, and competes with Herpes Virus Glycoprotein D for Herpesvirus Entry Mediator, a receptor expressed by T lymphocytes.

#### 10.2.3.1.3 Specimen Handling Requirements

The transmission of infectious agents may occur through contact with contaminated needles and blood or blood products. Consequently, appropriate blood and body fluid precautions should be employed by all study personnel involved in the collection of blood and handling of specimens in both the clinic and laboratory settings. Refer to current recommendations of the appropriate authorities.

In addition to appropriate handling of subject samples, specific regulations exist regarding the shipment of biologic samples. Procedures and regulations for the packaging and shipping of infectious samples are outlined in the site and/or study laboratory manual. The investigator is responsible for ensuring that all study samples that are to be transported to another location are appropriately packed and shipped per the applicable regulations.

#### **10.2.3.1.4 Evaluation of Laboratory Values**

The normal ranges of values for the central laboratory assessments in this study will be provided to each site as part of the lab manual. For assessments performed locally, the normal ranges of values for the local laboratory will be provided to the Sponsor's designee. They will be regarded as the reference ranges on which decisions will be made for the specific site.

If a laboratory value is out of the reference range, it is not necessarily clinically relevant. The investigator must evaluate the out-of-range values and record his/her assessment of the clinical relevance in the subject's source documentation.

All laboratory values which, in the investigator's opinion, show clinically relevant or pathological changes during or after termination of the treatment are to be discussed with the medical monitor, as necessary, and reported as AEs and followed, as described in Section [11.1.1](#).

All measurements described in this section are recognized standard methods.

#### **10.2.3.2 Clinical Examinations**

##### **10.2.3.2.1 Blood Pressure, Pulse Rate, Respiratory Rate, and Temperature**

Vital signs, including systolic and diastolic blood pressure, temperature, pulse, respiration rate, height, and bodyweight, will be collected as shown in the schedule of assessments (see [Table 1](#)).

Pre-dose vital signs should be taken within 60 minutes before dosing. Post-dose vital signs should be taken at least 60 minutes after dosing, prior to discharge. Additional blood pressure and pulse measurements may be performed, as determined by the investigator, to ensure appropriate monitoring of subject safety and accurate recording of vital sign measurements. Any changes from baseline deemed clinically significant by the investigator are to be recorded as AEs.

##### **10.2.3.2.2 Electrocardiogram**

A standard 12 lead ECG will be performed after the subject has been supine for approximately 5 minutes, at time points shown in the schedule of assessments (see [Table 1](#)). All ECG recordings will be identified with the subject number, date, and time of the recording and a copy will be included with the subject's source documentation.

All ECG values which, in the investigator's opinion, show clinically relevant or pathological changes during or after termination of the treatment are to be discussed with the medical monitor and reported as AEs and followed, as described in Section [11.1.1](#).

##### **10.2.3.2.3 Physical Examination, Weight, and Height**

A complete physical examination, including measurements of height and weight, will be conducted by a qualified licensed physician, physician's assistant, or a nurse practitioner at Visit 1 through Visit 9/ET (see [Table 1](#)). Any clinically significant physical examination findings are to be reported as AEs and followed, as described in Section [11.1.1](#). Height will be measured only at Visit 1.

#### **10.2.3.3 Adverse Events**

The investigator is responsible for the detection and documentation of events meeting the criteria and definition of an AE or SAE described below. At each visit, the subject will be allowed time to spontaneously report any issues since the last visit or evaluation.

Any clinically relevant observations made during each visit will also be considered AEs. AEs will

be collected from the time of informed consent through the last study visit.

#### **10.2.4 Immunogenicity Analyses**

Blood samples for ADA analysis will be collected at time points shown in the schedule of assessments (see [Table 1](#)). The Visit 2 sample is to be collected prior to dosing. Additionally, an ADA sample will be collected if an immunologically related AE is reported. Samples for ADA will be processed according to the methods and directions set forward in the laboratory manual(s) and guidance(s). ADA sample analysis will be performed by a laboratory defined in the laboratory manual(s) and guidance(s), according to their standard operating procedures (SOPs) using a validated method. Assay and analysis details will be described in the method validation and bioanalytical information.

#### **10.2.5 Pharmacokinetic, Pharmacodynamic and Biomarker Assessments**

Blood samples will be collected for assessment of PK, PD activity and mechanism of action of AVTX-002 in NEA.

Blood samples will be used to isolate serum, which will be subjected to analysis of soluble LIGHT levels in circulation using a relevant immunoassay for PD activity measures. Additionally, for a selected subset of sites or subjects, sputum samples will be analyzed for soluble LIGHT levels and gene expression. Biomarkers associated with inflammation such as (including but not limited to) IL-6, IFN- $\gamma$ , and TNF- $\alpha$  may be evaluated using relevant immunoassays. Serum may be also used for novel biomarkers analyses as the rationale evolves.

Blood samples collected for PBMC isolation may be used for comprehensive immunophenotyping of immune cell subsets in circulation by flow cytometry or CyTOF to study the effects of AVTX-002 on these cell types. Furthermore, transcriptomic analysis may be performed in PBMC as needed.

All these exploratory biomarkers as listed in [Table 1](#) will be performed at the laboratories specified in the laboratory manual(s) and/or guidance(s).

### **11 ADVERSE EVENTS**

#### **11.1 Definition of Adverse Events, Period of Observation, Recording of Adverse Events**

##### **11.1.1 Adverse Event Collection**

An AE is defined as any untoward medical occurrence in a patient or clinical investigation subject administered a pharmaceutical product that does not necessarily have a causal relationship with the product. An AE can therefore be any unfavorable and unintended sign (including a new, clinically important abnormal laboratory finding), symptom, or disease, temporally associated with the product, whether related to the product. An AE will be considered treatment-emergent if it occurs after the first dose of investigational product and within 28 days of a subject's last dose of investigational product. Additionally, an AE that occurred prior to dosing with study medication and increased in severity after start of dosing and within 28 days of a subject's last dose of investigational product will also be considered treatment emergent.

All AEs are collected from the time of the informed consent is signed until the end of study (Day 98/ET). This includes events occurring regardless of whether investigational product is administered. Note: Clinically significant observations noted during screening procedures (labs, physical examination, vital signs, etc.) should be entered as medical history. Only if the clinically

significant observation is clearly related to the performance of a screening procedure should it be entered as an AE (e.g., a hematoma because of drawing blood for screening labs). Where possible, a diagnosis rather than a list of symptoms should be recorded. If a diagnosis has not been made, then each symptom should be listed individually.

All AEs must be followed to closure, regardless of whether the subject is still participating in the study. Closure indicates that an outcome is reached or stabilization achieved (i.e. the investigator does not expect any further improvement or worsening of the event). When appropriate, medical tests and examinations are performed so that resolution of an event(s) can be documented.

Events that meet the protocol definition of an asthma related event are captured as part of the primary efficacy endpoint for the study, and therefore need not be recorded as an AE unless they meet the definition of an SAE. Asthma exacerbations that do not meet the protocol definition of an asthma related event should be captured as AEs.

An AE that changes in severity over time should be recorded in the eCRF once at the highest severity with two exceptions:

- Worsening of non-NEA-related pre-treatment events after initiation of investigational product must be recorded as new AEs. E.g., if the subject experiences mild, intermittent headaches prior to dosing with investigational product; however, the headache intensity increases to moderate after the first dose of investigational product, a new AE of moderate intermittent headaches is to be recorded in the source documents and eCRF.
- An AE which begins as a non-serious event, which later meets the definition of an SAE, should be entered once for the non-serious portion of the AE, and then be re-recorded as a new event with the start date the day it became serious.

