10.6 Efficacy

The following subject listings will be provided, using the FAS (observed as well as change from baseline values will be included as applicable):

- Occurrence of asthma related events – based on programmatic derivations from raw data (including the specification that constitutes the asthma related event – see [Section 6.2.1](#), date of first administration of study drug, first date of asthma related event/date of last subject visit, the applicable baseline definition – see [Section 9.2](#), time to first asthma related event/time to censoring in days)
- Individual daily recordings for peak flow measurements and number of SABA reliever puffs for subjects with an asthma related event; record/s where criteria for an asthma related event were met, will be flagged in this listing
- Occurrence of asthma related events – based on Investigator assessment (including the specification that constitutes the asthma related event – see [Section 6.2.1](#), date of first administration of study drug, first date of asthma related event/date of last subject visit)
- Discordance between programmatic derivation from raw data and Investigator assessment in occurrence of asthma related events

- FEV₁ (FEV₁ [L]) and FeNO (nitric oxide level [ppb]) results
- ACQ results (results for each individual item as well as the overall score – see [Section 6.2.4](#))
- AQLQ(S)+12 results (results for each individual item as well as the domain and overall scores – see [Section 6.2.5](#))
- ASD results (see [Section 6.2.6](#)) – this will include the following:
 - mean symptom scores for each symptom separately, as well as mean ASD scores, for each 1-week period
 - number of SABA reliever puffs (mean daily puffs/inhalations over each 1-week period)
 - peak flow measurements (mean measurement over each 1-week period)

Note: Only the weekly mean data are presented by subject in these subject listings; all individual daily recordings are however available in the submission datasets.

- EQ-5D-5L results (results for each of the 5 dimensions as well as for the EQ VAS – see [Section 6.2.7](#))
- PGI-C/S and CGI-I/S results (results for each question – see [Section 6.2.8](#) and [Section 6.2.9](#))

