10.6.1 Primary Endpoint Analysis

The primary endpoint analysis is performed using the assessments for the occurrence of asthma related events based on programmatic derivations from raw data.

The proportion of subjects who experience any asthma related event will be summarized by treatment group, also including the proportion of subjects who experience each of the 5 separate criteria for an asthma related event (as identified in [Section 6.2.1](#)). A subject who experienced multiple asthma related events will be counted once in each of the applicable criteria categories and once for having an asthma related event.

Summary statistics showing the number and percentage of subjects with and without asthma related events in each treatment group will be provided via a 2x2 table. Comparison of the proportions of subjects who had an asthma related event will be via a Wald Z-test (including and without continuity correction). The test statistic, its associated p-value and a 95% confidence interval for the treatment difference will also be provided.

The summary table and associated statistical analysis of the occurrence of asthma related events will be repeated for results obtained using each of the 4 baseline values for mean daily number of SABA puffs/inhalations and mean peak flow rate calculated according to Definitions 1 to 4 in [Section 9.2](#), for all subjects in the FAS. In addition, the results for occurrence of asthma related events using the baseline values for mean daily number of SABA puffs/inhalations and mean peak flow rate calculated according to Definition 1 in [Section 9.2](#), for subjects in the Per Protocol Analysis Set, will also be presented.

Figures (one per subject) will display the % change from baseline in peak flow rate and change from baseline in daily number of SABA puffs/inhalations over time. Baseline values calculated according to Definition 1 in [Section 9.2](#) will apply. Occurrence of the following will also be

indicated on the figure for each subject: administration of each dose of study drug, reduction of fluticasone dose, discontinuation of salmeterol and fluticasone, end of study participation. As part of the figure, information on subject disposition (whether the subject completed the study or reason for early discontinuation from the study) and whether any criteria for occurrence of an asthma related event were met, will also be displayed.

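### The AE recording rules can leave some asthma worsening out of the TEAE tables: a pre-dose asthma AE that worsens stays on one peak-severity record, and a site-called event that the program rejects has no stated route back to the AE page

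*Protocol*

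**What the plan says.** **Recording a change in severity.** Protocol 11.1.1 sets the general rule: "An AE that changes in severity over time should be recorded in the eCRF once at the highest severity with two exceptions". The first exception is "Worsening of non-NEA-related pre-treatment events after initiation of investigational product must be recorded as new AEs". The second covers an AE that turns serious, which is "re-recorded as a new event with the start date the day it became serious"; this one applies to asthma events as well.

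**Treatment emergence.** The TEAE definition in the same section has a worsening clause: "Additionally, an AE that occurred prior to dosing with study medication and increased in severity after start of dosing", within 28 days of the last dose, also counts. SAP 10.7.1 repeats the clause and adds that a pre-dose AE recurring after dosing at unchanged severity does not count. Neither text excepts asthma.

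**Asthma events as AEs.** Under Protocol 11.1.1, events that meet the asthma-related-event definition are captured in the primary endpoint and "therefore need not be recorded as an AE unless they meet the definition of an SAE". The companion rule is "Asthma exacerbations that do not meet the protocol definition of an asthma related event should be captured as AEs".

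**Who decides the endpoint.** SAP 10.6.1 states: "The primary endpoint analysis is performed using the assessments for the occurrence of asthma related events based on programmatic derivations from raw data". SAP 6.2.1 says the investigator's own assessment is recorded at each visit. SAP 10.6 plans a listing of those assessments and another titled "Discordance between programmatic derivation from raw data and Investigator assessment in occurrence of asthma related events". Neither document states an action that follows from the discordance listing.

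**The concern.** Salmeterol stops at Day 14 and fluticasone at Day 42 in subjects whose asthma is already poorly controlled. Asthma worsening is therefore the most foreseeable safety event, and safety is a secondary objective. Two features of the plan can keep some of it out of the by-arm TEAE tables.

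First, the rule on how many records a changing AE receives does not supply what the TEAE definition needs when the AE is asthma. The definition includes the event, but the record may not allow the derivation to recognise it.

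Second, the AE exemption rests on the event being captured in the primary endpoint. The site applies the exemption in real time, while a program decides later whether the event is in the endpoint. Where the two disagree, the reason for the exemption no longer holds and no stated rule restores the AE record.

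The tables at stake are TEAE incidence, maximum CTCAE grade and drug-related TEAEs. A pre-dose onset date also has a side effect: SAP 10.7.1 treats a missing causality rating as not related when the start date precedes first dose, and as probably related otherwise.

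**Working it through.** The plan states no figure on this point, so the check is of logic.

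**Part 1: can the worsening clause be applied?**

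Inputs: first dose on Day 1 and last dose on Day 57 (SAP Section 8 numbering, all three doses given), with a 28-day window. A record is flagged on its start date if 1 ≤ start day ≤ 57 + 28 = 85. The event days below are illustrative.

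| What is recorded | Start-date test | Flagged |
|---|---|---|
| One record: start Day -10, grade 2 (worsened after dosing) | -10 < 1 | No |
| Two records: Day -10 grade 1; Day 20 grade 2 | 1 ≤ 20 ≤ 85 | Yes |
| Event turns serious and is re-recorded at Day 20 | 1 ≤ 20 ≤ 85 | Yes |

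The first row could be rescued only by the worsening clause, which needs the grade before dosing and evidence of a later increase. Consider two histories:

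- Grade 1 from Day -10, rising to grade 2 on Day 20. This is treatment-emergent.
- Grade 1 from Day -10, rising to grade 2 on Day -5 and no further. This is not treatment-emergent.

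Under the single-record rule both become the same entry: start Day -10, grade 2. The clause cannot tell them apart from that record, and the SAP names no other source. For a pre-treatment event unrelated to NEA the first exception forces a second record and the problem does not arise.

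A new asthma AE starting at or after controller withdrawal is not affected. Withdrawal runs from Day 15 to Day 43 in SAP numbering, and 1 ≤ 15 and 43 ≤ 85, so an onset in that period is flagged in the ordinary way.

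**Part 2: site call against program call, for a non-serious exacerbation**

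| Site | Program | Primary endpoint | AE page |
|---|---|---|---|
| Yes | Yes | Counted | Optional |
| No | Yes | Counted | Should be entered |
| No | No | Not counted | Should be entered |
| Yes | No | Not counted | Optional |

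Only the last row can fall through both. It is a realistic outcome: SAP 6.2.6.2 sets missing SABA entries to zero, and under SAP 9.2 (Definition 1) a subject can have a null SABA or missing peak-flow baseline. One type of event is protected. For an emergency room visit not reported as an SAE, SAP 6.2.1 uses the investigator's assessment as the source, so the program does not overrule it.

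**Size.** One missed subject in an arm of 40 is 1/40 = 2.5 percentage points of TEAE incidence. The number of such subjects cannot be computed: the documents give no rate of run-in asthma AEs, of their worsening, or of discordance.

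**The case against.** The strongest reply is that both gaps are narrow and neither hides the event.

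Part 1 needs an asthma AE that starts before dosing, is still open, worsens, stays non-serious and does not become an endpoint event. The pre-dose start date is the natural reading of a single record, but it is inferred. The eCRF may hold a dated severity history; its design and completion guidelines are not in the documents. The record also stays in the all-AE listing and in the any-AEs row of the overall summary. All of this stands and limits the point, but it does not remove the conflict between the recording rule and the TEAE definition.

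Part 2 concerns events that may be lost, not events that must be. The exemption is permissive, SAEs are always recorded, inpatient hospitalizations are SAEs, and sites are told to record exacerbations that fall short of the definition. SAP 6.2.1 has the sponsor confirm atypical systemic-corticosteroid cases. Protocol 13.3.2 provides for consistency checks and site queries under a data management plan that is not shown, so some reconciliation may happen in practice. That also stands; what is missing is a stated rule.

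A reader might infer that the safety objective cannot be answered for asthma. The documents do not support that. Asthma worsening is compared by arm through the primary endpoint and each of its five criteria, the time-to-event analysis, FEV1, ACQ, the symptom diary, SABA use and peak flow. A reader might also infer that new exacerbations after controller withdrawal are lost through Part 1; the date check shows they are not.

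**Conclusion.** The point holds in a limited form. In Protocol 11.1.1 the single-record rule, with its exception confined to events unrelated to NEA, leaves the worsening clause of the TEAE definition without the data it needs for a continuing, non-serious asthma AE. Separately, a non-serious event that the site calls, does not enter as an AE, and the program rejects is in neither the primary endpoint nor the TEAE tables. It remains visible by subject in the investigator-assessment and discordance listings.

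The consequence is an incomplete TEAE tabulation of asthma worsening. Its extent is unknown, and any count of affected subjects would be a guess. The conclusion assumes that the single record keeps its pre-dose start date, that the eCRF holds no dated severity history, and that no unseen data-management step reconciles discordant events. If the last two are provided for elsewhere, the remaining work is to say so in the SAP. The change is worth making because it is cheap and because asthma worsening is the event these tables are most likely to be read for.

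**What to change.** 1. In Protocol 11.1.1 and the eCRF completion guidelines, reconcile the recording rule with the TEAE definition. Require a new record, or a dated severity change, for an NEA-related pre-treatment AE that worsens after first dose. Except worsening that meets the asthma-related-event definition and is exempt under the same section. Simply deleting the limit to events unrelated to NEA would not do, because it would make AE records mandatory for endpoint events that the section exempts.

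2. In SAP 10.6, add a step before unblinding. Using the planned discordance listing under baseline Definition 1, query the site on each investigator-yes, program-no event that has no AE record. Events that the investigator then confirms as an asthma exacerbation or worsening are entered as AEs with onset, grade, causality and outcome. Site review is needed because some of these calls may be simple miscounts against baseline and should not become AEs automatically.

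The cost is one wording change, one query round from a listing already planned, and a few more AE records.
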